Division of Internal Medicine
Department of Vascular Diseases

[name]
[name]
T [name]
F [name]
E [contact]
W www.kclj.si

Date: January 26, 2019

Study Protocol and Statistical Analysis Plan

Arterial Function and Atherosclerosis in Patients With JAK2 V167F Positive Essential Thrombocythemia

Principal Investigator: [name], PhD,
Professor of Medicine,
Head, Department of Vascular Diseases

Funding: Project No. TP20180038, financed by the Fund for Tertiary Research and Development of the University Medical Centre Ljubljana

1. Overview and Aim of the Study

We will study patients with JAK2 V617F positive essential thrombocythemia (ET) without clinically apparent atherosclerotic vascular disease in comparison to age-and sex-matched, apparently healthy control subjects and measure changes in vascular function and morphology at baseline and after a 4-year observation period. In addition, the JAK2 V617F allele burden, i.e., the percentage of mutated alleles in leukocytes, will be determined and correlated with vascular function and morphology. The study protocol has been approved by the Committee for Medical Ethics of the Republic of Slovenia, approval number: 0120-428/2017/4.

Our aim is to test (a) whether changes in vascular function and morphology in a 4 year observation period differ between patients with JAK2 V617F positive ET in comparison with control subjects, and whether (b) the JAK2 V617F allele burden correlates with vascular function and morphology.

2. Patients and Control Subjects

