Patients with JAK2 V617F positive ET have been selected from the database of the Department of Hematology of the University Medical Centre Ljubljana, Slovenia, after having given their informed consent. Only patients without a personal history of clinically manifest atherosclerotic vascular disease (myocardial infarction, angina pectoris, peripheral arterial disease, aortic disease, transient ischemic attack or ischemic stroke) were eligible. The control group has been selected among apparently healthy employees of the University Medical Centre Ljubljana and their relatives. The groups have been matched for age and sex distribution and classical risk factors for cardiovascular disease. Forty patients (14 male and 26 female) with JAK2 V617F positive ET without clinically apparent cardiovascular disease were enrolled in the study in 2014 - 2015 for the first examination and 36 (12 male and 24 female) of them are expected to participate also in 2018-19. Forty two control subjects (16 male and 26 female) participated in the first examination in 2014-2015 and at least 38 (14 male and 24 female) subjects are expected to participate in the second examination.

Inclusion criteria for patients are: clinically confirmed ET with genetically confirmed JAK2 V617F mutation, age above 18 years, absence of clinically suspected or overt atherosclerotic vascular disease. For the control subjects, the inclusion criteria are being apparently healthy, matching the patients in age and sex, age above 18 years, and absence of clinically suspected or overt atherosclerotic vascular disease.

Exclusion criteria for both groups are: clinically suspected or overt atherosclerotic vascular disease, chronic kidney disease stage 3 and above, known cancer, chronic inflammatory disease, autoimmune disease, and pregnancy.

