Differences between subjects with ET and control subjects at the first and second examination will be tested by the chi-square test for discrete variables, for normally distributed continuous variables by the paired Student's t-test for independent samples, and for non-normally distributed continuous variables by the Mann-Whitney test for independent samples. P-values of < 0.05 will be considered significant with a correction for multiple comparisons.

Changes in vascular function and morphology in the 4-year observation period will be compared between the two groups by the log rank test. P-values of < 0.05 will be considered significant.

The association between the parameters of vascular function / morphology and the JAK2 V617F allele burden will be assessed by the Pearson correlation coefficient.

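### Aim (a) is to be answered by a log rank P-value alone: Section 7 plans no between-group difference in 4-year change and no confidence interval.

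*Combined protocol and SAP*

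**What the plan says.** Section 1 sets aim (a) as testing "whether changes in vascular function and morphology in a 4 year observation period differ between patients" and controls. Section 7 answers it in two sentences: "Changes in vascular function and morphology in the 4-year observation period will be compared between the two groups by the log rank test", followed by "P-values of < 0.05 will be considered significant". The comparisons at each separate examination have their own rule: "P-values of < 0.05 will be considered significant with a correction for multiple comparisons".

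For presentation, Section 7 plans mean and SD for normally distributed data and median and quartiles otherwise. It does not say whether these summaries apply to the 4-year change or only to the values at each visit. For aim (b) it names the Pearson correlation coefficient and attaches no significance rule.

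No section plans a between-group difference, a ratio, a confidence interval, a margin, a sample-size rationale, or a rule for reading a non-significant result.

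Section 2 gives the numbers. At the first examination: "Forty patients (14 male and 26 female) with JAK2 V617F positive ET" and "Forty two control subjects (16 male and 26 female) participated in the first examination in 2014-2015". For the second, of the patients "36 (12 male and 24 female) of them are expected to participate also in 2018-19", and of the controls "at least 38 (14 male and 24 female) subjects are expected to participate in the second examination".

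**The concern.** Aim (a) is a question about a difference in change. A reader of the results will want to know how large that difference is and how well it has been measured. A log rank P-value gives neither. If it falls below 0.05, the plan attaches no size to the finding. If it does not, the plan offers nothing to show whether the groups changed alike or the study was too small to tell.

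This matters more than usual here because the cohort was fixed by enrolment in 2014-2015. Sample size cannot be raised, so what is estimated and how it is read are the remaining safeguards.

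**Working it through.** The plan states no power, effect size or SD, so it has no figure to reproduce. The log rank test is named without an event or a time to event, so its power cannot be computed from the documents. The calculation below asks instead how precise an ordinary comparison of change scores would be with the expected numbers.

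**Inputs**
- Patients at the second examination: n1 = 36 (Section 2).
- Controls at the second examination: n2 = 38, the stated minimum (Section 2).
- Alpha 0.05 (Section 7). Sidedness is not stated; two-sided is assumed because the aim is worded as a difference.
- Assumed: change scores roughly normal, equal SDs in the two groups, SD set to 1.

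**Precision**
- SE = sqrt(1/n1 + 1/n2) = sqrt(1/36 + 1/38) = 0.2326 SD.
- Degrees of freedom = 36 + 38 - 2 = 72, and t(0.975, 72) = 1.993.
- 95% half-width = 1.993 x 0.2326 = 0.464 SD.

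**Chance of P >= 0.05** (noncentral t, 72 df, noncentrality = true difference / SE)

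| True difference | Noncentrality | Chance of P >= 0.05 |
|---|---|---|
| 0.4 SD | 1.72 | 60% |
| 0.5 SD | 2.15 | 44% |
| 0.66 SD | 2.84 | 20% |

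So 80% power is reached only at about 0.66 SD.

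**What the interval would add**
- Observed difference 0: interval -0.46 to +0.46 SD.
- Observed difference 0.4 SD: P = 0.09, interval 0.4 +/- 0.464 = -0.06 to +0.86 SD.

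Both results are non-significant under the planned rule, yet they say different things. Only the estimate and interval show that.

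**Sensitivity to retention.** If everyone enrolled returned (40 and 42), the half-width would be 0.44 SD, power at 0.5 SD 61%, and the difference detectable with 80% power 0.63 SD. The conclusion does not depend on the few expected losses.

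**Check on the choice of estimator.** The carotid plaque score runs from 0 to 6 (Section 4.1), so many changes will be tied at zero. This was simulated for 36 against 38 subjects, with progression of 1 or 2 points in 40% against 20% (assumed rates). The Hodges-Lehmann estimate was 0 in about 98% of runs, and its 95% interval collapsed to 0 to 0 in about 64%. At 30% against 20% it collapsed in about 95%. That estimator would show false certainty for such a measure, so the fix treats tied measures separately.

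**The case against.** Four objections carry weight.

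1. A reader might infer that the investigators intend to report a non-significant result as no difference. No section says so. Section 7 states only what counts as significant. The misreading is a risk that the plan leaves open, not a rule that it contains.

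2. A reader might infer that everything in Section 7 rests on P < 0.05 alone. That fits the change comparison only. The comparisons at each examination carry an unspecified correction for multiple comparisons. For normally distributed measures at those visits, the group means, SDs and numbers also let a reader work out a difference and interval by hand. This does not rescue aim (a): SDs at each visit do not give the SD of change without the within-person correlation, medians with quartiles give no standard interval, and the plan does not say that change will be summarised.

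3. A reader might infer that aim (b) has the same defect. It does not. Pearson's r is itself an effect size, no P-value rule is attached to it, and an approximate interval follows from r and n. With 36 patients, r = 0.20 has a 95% interval of -0.14 to 0.50. Printing it would help, but its absence from the plan is minor.

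4. The SD-unit figures describe a t-test that the plan does not use for change. This stands, and 44% must not be quoted as the miss rate of the planned analysis. The documents also give no clinically relevant difference, so they do not say whether 0.5 SD matters for any measure. The figures show only what a sample of this size can resolve.

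**Conclusion.** The point holds for aim (a). Its planned result is a log rank P-value judged at 0.05, with no difference in change and no interval. That output could not separate absence of a difference from low precision. Precision is limited: about +/-0.46 SD for a difference in change, with a true 0.5 SD difference missed about 44% of the time. These figures assume a two-sided t-test on roughly normal change scores, equal SDs, and 36 and 38 subjects returning.

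The missing event and time definition for the log rank test is a separate and more basic problem. Correcting the test alone would still leave an answer consisting of a P-value. The change is one the sponsor should make: it does not affect the data, but the conclusion on aim (a) depends on it.

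**What to change.** In Section 7, replace the log rank P-value as the result for aim (a) with the ET-minus-control difference in 4-year change and its 95% confidence interval, for each vascular measure:

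- **Roughly normal measures:** the difference in mean change.
- **Skewed continuous measures with few ties:** the Hodges-Lehmann shift.
- **Heavily tied measures** (the carotid plaque score, and the Agatston score if many values stay at zero): the difference in the proportion who progress, with progression defined in advance, or the difference in mean change with a bootstrap interval.

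Take each P-value from the test that matches the estimate, so that the two do not come from different analyses. Add a sentence in this sense: a result with P >= 0.05 is reported with the range of differences that the interval does not exclude, and is not described as absence of a difference.

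A 95% interval for each correlation in aim (b) is an optional small addition. These intervals are per measure and do not settle multiplicity across measures.

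The cost is revised SAP wording and a little more analysis, with no extra patients, visits or measurements. The downside is that null results will be stated less firmly.

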All subjects will be examined twice, the first time in 2014 - 2015 and the second time in 2018 – 2019. All participants will have signed the informed consent form before enrolment. The subjects will complete a structured questionnaire about personal and family medical history, risk factors for cardiovascular disease and their medication. They will be physically examined and will donate blood samples for laboratory tests. Ultrasound examination of the extracranial carotid arteries will be done, and echo-tracking of the common carotid arterial wall will be used to assess the β-stiffness index and to estimate the pulse wave velocity. EndoPat plethysmography will be used to assess the endothelial function via the reactive hyperemia response of the digital arteries. Coronary artery calcium scanning will be performed to evaluate the extent of coronary artery calcification.

3. Baseline Measurements

Every participant will be examined physically, including measurements of height, weight, waist circumference, systolic and diastolic blood pressure. Blood will be taken for laboratory analyses - electrolytes, complete blood cell count, serum lipids, liver function tests, urea, creatinine, inflammatory markers and DNA

isolation for measurement of JAK V617F allele burden. A structured questionnaire about family history of cardiovascular diseases, personal medical history, smoking status and medications will be completed. The 10-year risk of coronary heart disease (CHD) and general cardiovascular disease (CVD) will be calculated using the Framingham risk equation.

4. Vascular Imaging

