4.1. Carotid Artery Ultrasound Examination

For examination of the extracranial carotid arteries an ultrasound machine Aloka Prosound a7 (Hitachi Aloka Medical, Ltd., Japan) will be used with a linear vascular probe working at a frequency of 5-13 MHz. The common, internal and external carotid arteries on both sides will be examined. At each examination, the measurements will be done twice and their average values will be calculated. The ultrasound examination will be done by the same ultrasonographer at both visits of all participants.

The intima-media thickness will be measured 2 cm proximal to the bulb of common carotid artery on both sides. Screening of the extracranial carotid arteries for atherosclerotic plaques will be performed, with a plaque definition of a focal lesion, exceeding the intima-media thickness for at least 50% or reaching an absolute thickness of at least 1.5 mm in two orthogonal projections. Scoring of atherosclerotic plaques is done according to the methodology from the Rotterdam Study. The presence of at least one plaque in each segment of the extracranial carotid arterial bed, (divided into the common carotid artery and the bulb, the internal carotid artery and the external carotid artery) on either sides is scored 1 point. Thus, the carotid plaque score ranges from 0 (absence of plaques) to 6 (plaques present in all segments on both sides).

Echo-tracking of the common carotid artery will be used to assess arterial stiffness expressed by the β -stiffness index and the pulse wave velocity. Measurements will be done at the common carotid artery 2 cm proximal to the bulb on both sides. The β -stiffness index will be calculated as: $\beta = \ln(P_{\max} / P_{\min}) / [(D_{\max} - D_{\min}) / D_{\min}]$, where P_{\max} = the systolic blood pressure, P_{\min} = the diastolic pressure; D_{\max} = the maximum arterial diameter and D_{\min} = the minimal arterial diameter. Pulse wave velocity (PWV) will be calculated as: $PWV = \sqrt{((\beta \times P_{\min}) / 2\rho)}; \rho = 1050 \text{ kg/m}^3$.

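### The 4-year changes of aim (a) are to be compared by the log-rank test, but the study has two visits, measured outcomes and no defined event

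*Combined protocol and SAP*

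**What the plan says.** Section 1 sets aim (a) as testing "whether changes in vascular function and morphology in a 4 year observation period differ between patients with JAK2 V617F positive ET" from those in controls. Section 2 fixes the design: "All subjects will be examined twice, the first time in 2014 - 2015" and the second in 2018–2019. It expects 36 of 40 patients and at least 38 of 42 controls at the second examination.

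Sections 4 and 5 define the outcomes. They are intima-media thickness, a carotid plaque score from 0 to 6, the β-stiffness index, pulse wave velocity, the Agatston score, the reactive hyperaemia index and the augmentation index. A typical definition is "The intima-media thickness will be measured 2 cm proximal to the bulb of common carotid artery on both sides".

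Section 7 then states: "Changes in vascular function and morphology in the 4-year observation period will be compared between the two groups by the log rank test". The preceding paragraph of Section 7 covers the other group tests: "Differences between subjects with ET and control subjects at the first and second examination will be tested by the chi-square test" for discrete variables, and by a t-test or Mann-Whitney test for continuous ones.

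**The concern.** The log-rank test compares the times at which an event occurs. The change in intima-media thickness or Agatston score between two visits is a quantity, not an event with a date. The plan names no event, progression threshold, time origin or censoring rule. The plaque definition in Section 4.1 feeds a score, and a new plaque would be known only to have arisen at some point between the two visits.

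The chi-square, t and Mann-Whitney tests are tied to each examination separately. They compare levels, so they do not answer aim (a). The log-rank sentence is the only analysis that addresses change.

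Two things are at stake. The analyst would have to invent an event rule, and could do so after seeing the data. And no version of the test returns what aim (a) asks for, a between-group difference in change, in the units of the measure, with a confidence interval.

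**Working it through.** The documents give no SD, effect size, power or event count, so there is no stated figure to reproduce. The mismatch itself follows from reading Sections 1, 2, 4, 5 and 7 together. The calculations show what happens if the test is forced onto these data.

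**Inputs from the plan:** 36 patients and 38 controls at the second visit (Section 2); significance level 0.05 (Section 7), taken as two-sided because sidedness is not stated.

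**Assumed:** normally distributed changes, a true difference of 0.66 SD of change, and the event counts, control mean changes and visit intervals named below.

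**1. Reference analysis: t-test on changes.**
- Standard error in SD units: √(1/36 + 1/38) = 0.2326.
- Difference detectable with 80% power, normal approximation: (1.960 + 0.842) × 0.2326 = 0.652 SD. With the noncentral t distribution it is 0.660 SD, which is why 0.66 is used.
- 95% CI half-width: t(0.975; 72) × 0.2326 = 1.993 × 0.2326 = 0.464 SD.

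**2. Progressor event, all second visits at one nominal time.** With a of n₁ and b of n₂ subjects progressing, m = a + b and N = n₁ + n₂:
- E = m·n₁/N, V = m(N − m)n₁n₂ / [N²(N − 1)], statistic = (a − E)²/V.
- For an assumed 12/36 versus 6/38: E = 18 × 36/74 = 8.757; V = 18 × 56 × 36 × 38 / (74² × 73) = 3.450; statistic = (12 − 8.757)²/3.450 = 3.049.
- Pearson chi-square for the same 2×2 table is 3.091, and 3.091 × 73/74 = 3.049.

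The log-rank test is then a 2×2 comparison with no timing information.

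**3. Progressor event dated at the actual second visit.** Subjects above the median change have an event on their visit date and the others are censored on theirs. The spacing of visits then enters the statistic.

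**4. The change itself used as an uncensored time.** This is a computable rank test. In 20,000 simulated datasets its type I error was 0.054, but the result depends on the sign convention. Reversing the sign of the change switched significance in 27% of datasets at a difference of 0.5 SD and in 23% at 0.66 SD.

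**Simulated power at 0.66 SD** (40,000 datasets per setting):

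| Analysis | Power |
|---|---|
| t-test on changes | 80% |
| Mann-Whitney test on changes | 78% |
| Log-rank, change as time | 73% |
| Log-rank, above-median change, one nominal time | 56% |
| Log-rank, any increase, one nominal time; control mean change 0, +0.5, +1, +1.5 SD | 59%, 49%, 32%, 15% |
| Log-rank, above-median change, actual visit date (interval SD 0.25–0.5 year) | about 33% |

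**False-positive rate of the visit-date version** with no true difference in change: about 5% if mean intervals are equal, 8–22% if they differ by 1 month, and 29–83% if they differ by 3 months.

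**The case against.** No passage supplies an event rule, so the defence concerns emphasis. Its points are these.

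- **The power deficit depends on the distribution.** This stands. With skewed changes the change-as-time log-rank test can match or beat the alternatives. For exponential changes with a scale ratio of 2, one run gave log-rank 0.83, t-test 0.82 and Mann-Whitney 0.71. Section 7 does foresee non-normal data. But reversing the sign of the change cuts that log-rank power to 0.50, and the plan states no sign convention. The power figures therefore apply to normal changes only.
- **The visit-date false positives are conditional.** This also stands. They need an implementation that the plan does not describe and unequal visit spacing that it does not suggest, since both groups share the same calendar windows. The largest figure is for a 3-month gap with an interval SD of 0.25 year, a full SD of separation. Unequal follow-up could also bias a plain comparison of changes if change builds up with time.
- **It may be a slip for a rank-sum test.** This is possible. The same section calls a t-test both paired and for independent samples. But nothing in the text says which test was meant, and the sentence governs the first aim, so it needs correcting either way.
- **The sizes have no anchor in the plan.** True. The 0.66 SD is simply the difference at which the t-test has 80% power. The figures rank possible implementations and do not measure harm in this trial.

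**Conclusion.** The concern holds. The method assigned to aim (a) does not fit the data to be collected and is undefined without rules that the plan lacks. This is an error in the stated method and must be fixed before the change analysis is run. The conclusion rests on the text alone and needs none of the simulations.

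The size is illustrative. It assumes 36 versus 38 subjects, normal changes, a two-sided 0.05 level and a true difference of 0.66 SD. Power then falls from 80% for a t-test on changes to between 15% and 73%, depending on how the log-rank test is forced. The t-test would also give a 95% CI of about ±0.46 SD of change, which the log-rank test does not provide. The visit-date false-positive rates hold only under the assumed gaps in visit spacing.

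**What to change.** Delete the log-rank sentence in Section 7 and put in its place:

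> For each vascular measure, the individual change (second minus first examination) will be compared between groups by the unpaired two-sample t-test if normally distributed, or by the Mann-Whitney test otherwise (including the plaque score and the Agatston score). The between-group difference in change will be reported with its 95% CI (mean difference, or Hodges-Lehmann estimate).

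Two additions are optional:

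- For the continuous measures, a two-visit linear mixed model with a group-by-visit interaction targets the same difference and keeps all 40 + 42 = 82 baseline participants. The gain is modest, since only 82 − 74 = 8 are expected to lack a second visit.
- Analysis of covariance on the baseline value should be a sensitivity analysis only. The groups are matched, not randomised: "The control group has been selected among apparently healthy employees of the University Medical Centre Ljubljana and their relatives". With a stable baseline gap of 0.5 SD and no difference in change, it rejected in 22%, 14% and 7% of simulated datasets at between-visit correlations of 0.5, 0.7 and 0.9, against about 5% for the t-test on changes.

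Reporting the interval between visits by group would show whether unequal follow-up is an issue. The cost is SAP wording only, with no new data, visits or participants.

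### No multiplicity correction is stated for the 4-year change comparisons that answer aim (a), and no primary change outcome is named

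*Combined protocol and SAP*

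**What the plan says.** Aim (a) in Section 1 is to test "whether changes in vascular function and morphology in a 4 year observation period differ between patients" with JAK2 V617F positive essential thrombocythemia and controls. It names no single measure.

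Section 7 gives two significance rules in adjacent paragraphs:

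- For group differences at the first and at the second examination: "P-values of < 0.05 will be considered significant with a correction for multiple comparisons". Neither the method nor the set of tests it covers is given.
- For the 4-year changes, compared between the groups: "by the log rank test. P-values of < 0.05 will be considered significant". Nothing is said about correction.

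Section 7 does not list the outcomes to which the change comparison applies. They have to be gathered from Sections 4 and 5:

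- Section 4.1: intima-media thickness ("The intima-media thickness will be measured 2 cm proximal to the bulb"), plaque score ("the carotid plaque score ranges from 0 (absence of plaques) to 6"), beta-stiffness index and PWV.
- Section 4.2: Agatston score.
- Section 5: reactive hyperaemia index (RHI) and augmentation index (AI).

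No section calls any of these primary, ranks them, or labels the change analyses exploratory.

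**The concern.** The comparisons that answer the study's first aim have the looser stated error control, while the single-visit comparisons have the tighter one. With several vascular measures and no named primary outcome, one isolated p-value below 0.05 among the changes could be reported as a positive answer to aim (a). The plan gives no rule for reading such a result. How far this raises the false-positive risk depends on how many change tests are run, and the plan does not state that number.

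**Working it through.** **Inputs from the documents.** Threshold 0.05 for the changes (Section 7). Seven vascular measures (Sections 4.1, 4.2 and 5). Expected at the second examination: patients, "36 (12 male and 24 female) of them are expected to participate also in 2018-19"; controls, "at least 38 (14 male and 24 female) subjects are expected to participate in the second examination".

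**Assumptions, not in the documents.** One test per measure, two-sided, each with a true size of 0.05, and the correlations shown below. The plan gives no familywise or power figure, so there is none of its own to reproduce.

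**Overlap of two measures.** Section 4.1 sets PWV = sqrt(beta × Pmin / 2ρ), so ln PWV = ½ ln beta + ½ ln Pmin + constant. PWV shares the beta term but also carries diastolic pressure. The two overlap without being identical. Their correlation was taken as 0.85, and six tests without PWV were run as an alternative.

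**Chance of at least one false positive.** For k independent tests it is 1 − 0.95^k. For correlated tests it comes from multivariate normal simulation with 2,000,000 draws per cell.

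| Change tests | Other pairs 0 | 0.3 | 0.5 | 0.7 | 0.9 |
|---|---|---|---|---|---|
| Seven (beta–PWV 0.85; all pairs 0.9 in last column) | 28.4% | 25.8% | 22.2% | 17.5% | 11.4% |
| Six (PWV left out) | 26.5% | 24.1% | 20.7% | 16.4% | 10.8% |
| Four (plaque and Agatston also left out) | 18.5% | 17.4% | 15.5% | 13.1% | 9.4% |
| Two | 9.75% | 9.5% | 9.1% | 8.4% | 7.0% |
| One composite | 5% | – | – | – | – |

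Exact checks at correlation 0: 1 − 0.95^6 = 0.265; 1 − 0.95^4 = 0.1855; 1 − 0.95^2 = 0.0975. With six tests the exact value sits at the 26%/27% rounding boundary.

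The four-test row also covers the case in which the plaque and Agatston tests never falsely reject. The plaque score is discrete and the Agatston score may have many zeros, so their true size may be below 0.05.

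**Power cost of correcting every change outcome.** This uses 36 versus 38 and a t-test approximation, since the plan names no t-test for changes. The standard error in SD units is sqrt(1/36 + 1/38) = 0.233. The noncentral t distribution with 72 degrees of freedom gives:

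| Alpha | Difference detectable with 80% power | Power at 0.66 SD |
|---|---|---|
| 0.05 | 0.66 SD | 80% |
| 0.05/6 = 0.0083 (strictest Holm step, six tests) | 0.83 SD | 55% |
| 0.05/7 = 0.0071 (strictest Holm step, seven tests) | 0.84 SD | 53% |

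A normal-approximation check at 0.05 gives (1.960 + 0.842) × 0.233 = 0.65 SD, consistent with the first row.

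**The case against.** The strongest reply is that the number of tests is not in the plan. Section 7 speaks of changes in function and morphology as a whole. A log-rank test needs an event and a time, and neither is defined. One composite progression event would mean one test and no inflation. One test for function and one for morphology would give 7% to 10%. This stands: the larger figures hold only if each measure is tested separately. It also means that the definition of the test comes first, because it fixes which tests form the family.

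A reader might infer that the plan expressly rules out correction for the changes. It does not. The qualifier appears in one paragraph and is absent from the next. That makes uncorrected testing the plain reading, but loose drafting is possible, since the same section describes a paired t-test for independent samples. Nor is the difference between the paragraphs a contradiction in itself. The corrected comparisons are not limited to vascular measures and could form a larger family.

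A reader might also take seven independent tests and quote 1 − 0.95^7 = 30%. Section 4.1 does not support that, because PWV is derived from beta. The opposite step, treating PWV as adding nothing, also fails, because diastolic pressure enters separately.

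Finally, this is a small observational cohort with no sample-size calculation, and reporting every outcome with estimates and intervals is a defensible approach. But the plan does not say that this is its approach. It sets a significance threshold for a stated aim.

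**Conclusion.** The point holds in conditional form. Section 7 states a correction for the single-visit comparisons and none for the change comparisons behind aim (a), and no primary outcome or exploratory label limits what one positive result may claim. If each measure's change is tested separately at a true size of 0.05, the chance of at least one false positive is roughly 11% to 28% for six or seven tests and 9% to 19% for four, over assumed correlations from 0.9 to 0. The documents do not support a single figure, nor an unconditional statement that the risk is well above 5%. The true size of the named test is also unknown until its event and time are defined. This is a cheap improvement, and it ranks after the question of which test is to be used.

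**What to change.** **Settle first, as a separate point.** Define the event and time for the log-rank test, or replace the test, so that the set of change comparisons is known.

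**Preferred change.** Before second-visit data are analysed, add text to Section 7 that:

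- names one primary 4-year change outcome, tested at 0.05;
- labels the other change outcomes exploratory and reports them with estimates and confidence intervals;
- states that first-visit data were already available when the choice was made.

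The cost is a text change, and the other outcomes cannot then support a confirmatory claim. Timing matters. The plan is dated January 2019, and Section 2 says "All subjects will be examined twice, the first time in 2014 - 2015 and the second time in" 2018–2019, so second visits may already be under way.

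**Alternative, at a larger power cost.** Extend the plan's own correction to the change comparisons, with a named method (for example Holm) and a listed family, and treat PWV as supportive of beta-stiffness. At the strictest step the detectable difference rises from 0.66 SD to about 0.83–0.84 SD, and power at 0.66 SD falls from 80% to 53–55%. If the sponsor meant the existing correction to carry over to the changes, one sentence saying so, with the method and family, would be enough.
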